3.3 Description of Study Design

This is an interventional, randomized, double-blind (participant and study staff), sham-controlled, parallel design, pilot study of N=80 RR-MS and SP-MS participants, characterized by mild to moderate gait dysfunctions. There will be a 1:1 random assignment of participants to receive either the active or the sham tDCS while performing the PA program. Blocked stratification will be used to randomize the participants to their respective study conditions. Block sizes of 4 and 6 will be used and the stratifying factor will be EDSS score (0-3.5 and 4.0-6.5). Randomization will be done by an independent randomizer who takes no part in baseline, follow-up, or sessions to maintain the double-blind nature of the study.

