3.4.2 Secondary Study Endpoints

- The feasibility of delivering at-home supervised PA paired with tDCS will be assessed using the number of completed sessions at-home. It will be considered as “feasible” when participant complete successfully at least 80% of the total at-home sessions
- Comparisons between the active and sham conditions at baseline and at the end of the study by assessing the changes in gait spatial-temporal parameters (stance, swing and double support phase; cadence; step width) and functional mobility parameters objectively assessed using wearable inertial sensors
- Comparisons between the active and sham conditions at baseline and participation end conditions by assessing the changes in scores of 9-item FSS (physical aspect of fatigue) and 21-item MFIS (physical 9 items, cognitive 10 items, psychosocial 2 items), MSWS-12 (subjective measures of impact for walking ability and related pathology), and MSQOL-54 (36 items for generic health-related quality of life measures and 18 items for MS-specific measures).
- Comparisons between the active and sham conditions at baseline and participation end conditions by assessing the changes in scores of VAS- F₀₋₁₀ (to assess the perceived general fatigue)
- Review of experiences of minor adverse events and pain ratings. In particular, participants will have to report and rate any adverse events. Pain ratings will be measured, using a VAS- P₀₋₁₀ (rating 1 for minimal to 10 for most severe), before and after each session (any experience of pain or other adverse event above an intensity rating of 7 will result in study discontinuation)
- Comparisons between the active and sham conditions at pre and post tDCS-PA session by assessing the changes in the performance of the cognitive tests and EEG signal changes during the time of testing
- Comparisons between the active and sham conditions at baseline and participation end conditions by monitoring the changes in level of daily physical activity and amount of sleep as measured by ActiGraph
- Comparisons between the active and sham conditions at baseline and participation end conditions by monitoring the changes in sway parameters as objectively measured by the instrumented Posturography test and by monitoring changes in total score Berg Balance Scale.
- Change in processing speed between baseline and immediately after the treatment end to assess improvement in cognitive function as indirect effect of aerobic PA.

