The inertial sensor will be attached at the lower lumbar level (positioned at the center at the L4-L5 intervertebral disc level) with a semi-elastic belt. The device acquires acceleration and angular velocity signals, which are transmitted in real time via Bluetooth to a PC.

Participants will repeat the test twice: the first trial serves mainly for familiarization, while the second is actually measured and the resulting data will be processed.

Device:

Wireless inertial sensor device G-sensor (BTS Bioengineering S.p.A., ITALY).
The wearable unit includes a tri-axial accelerometer, a gyroscope, and magnetometer.

- **Electroencephalogram (EEG) evaluation paired with cognitive testing (Optional)**

Participants may be asked to wear a miniature 3-electrode head strap device at the discretion of the study staff before and after the first and final tDCS session. The EEG measures the electrical activity in the brain and quantifies and assesses the effect of tDCS intervention. EEG signal analysis may introduce a novel approach in quantifying measurements associated with cognitive load, emotional states, stress, and pain.

During the EEG measurement period, participants will complete testing using the Cogstate Brief Battery, a validated computer-based platform{CogState, 2015 #95}{Maruff, 2013 #96}{Charvet, 2018 #462} that takes approximately 10 minutes to compute, and the Symbol Digits Modalities Test (SDMT) , a 90 second paper and pencil measure of symbol to number matching.{Smith, 1982 #82}{Charvet LE, 2014 #390}

Device:

Functional Brain Activity Sensor (fBAS™) is a sticker-size, sticker-thin, wireless sensor (medical grade accuracy) that uses three EEG electrodes (Neurosteer, LTD). fBAS device comprises of a EEG sensor and a Bluetooth transmitter. EEG recordings are collected by 3 medical grade electrodes on via a forehead patch, and the captured signals are sent via low energy Bluetooth to a PC for the real-time processing.

The EEG paired with Cognitive test assessment will be an optional measurement and will be at the study staff discretion when to perform these tests (limited time and/or limited availability of fBAS device).

- **ActiGraph Evaluation (Instrumented daily assessment of physical activity and sleep, i-DPAS)**

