5.3.2 Enrollment/Baseline (Visit 1)

- Obtain informed consent of potential participant verified by signature on study informed consent form
- Verify inclusion/exclusion criteria (Section 5.1)
- Obtain demographic information, medical history, medication history
- Neurology Exam/Obtain EDSS (If participant is outside of NYU)
- Assessment of weight, height, and BMI
- Baseline measure: gait assessment with instrumented 10-meter walk (i-10MW), functional mobility assessment with instrumented Time Up and GO (i-TUG), Timed 25-Foot Walk (T25-FW), instrumented 2 minute walk (i-2MW) test, balance assessment with static posturography test, administration of Berg Balance Scale, and administration of questionnaires (9-item FSS, 21-item MFIS, MSWS-12, 54-MSQOL, and VAS- F 0-10)
- Cognitive assessment using BICAMS and CogState brief battery
- Provide instructions for wearing the ActiGraph device (optional)
- First tDCS session

CONFIDENTIAL

This material is the property of the NYU School of Medicine and Langone Medical Center. Do not disclose or use except as authorized in writing by the study sponsor

Interventional Template Version: 28 APR 2017

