5.3.3 Intermediate Remote Visits (Day 2 to Day 10)

- Administer the study treatment for 9 visits
(Active stimulation: 20 mins of tDCS (2.5mA) while participants will complete physical training; Sham stimulation: 20 mins of tDCS sham stimulation, no current delivery during the session, while participants will complete physical training)
- Record adverse events as reported by participant with pain ratings (VAS- P₁₋₁₀) and self-reporting and rating possible adverse events during each stimulation session
- Monitoring of perceived exertion using Borg scale. Borg scale will be administered by study technician every 5 minutes during the 20 minutes PA training
- Instructions provided to participants after the session: no concurrent physical therapy for the entire duration of the study
- Optional: Only for the first (day 1) and follow-up (day 11) may participants' be asked to wear EEG electrodes. While performing cognitive tests (CogState and the SDMT) before and after the stimulation period, participant's EEG signals will be simultaneously recorded for ten minutes.

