7.1 Statistical Hypotheses

Research hypothesis

There is a significant difference between active and sham groups by comparing primary and secondary outcomes at baseline and end treatment time.

Null hypothesis

There will not be a significant difference between active and sham groups

CONFIDENTIAL

This material is the property of the NYU School of Medicine and Langone Medical Center. Do not disclose or use except as authorized in writing by the study sponsor

Interventional Template Version: 28 APR 2017

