Secondary	To determine the effect of the combination of the tDCS and PA on fatigue	Physical aspect of fatigue with 9-item FSS	1. Prior to treatment beginning 2. After treatment end 3. 4 weeks follow up	No
Secondary (Optional)	To determine the effect of tDCS on brain activity during the performance of cognitive test	Change in EEG signal before and after tDCS session	1. Prior to treatment beginning and after treatment end during Day1 and Day 10 visit	No
Secondary	To determine the globally effect of the combination of the tDCS and PA	Physical, cognitive and psychosocial aspect with 21-item MFIS	1. Prior to treatment beginning 2. After treatment end 3. 4 weeks follow up	No
Secondary (Optional)	To determine the effect of tDCS treatment on level of daily physical activity and sleep	Intensity of physical activity, daily step count and number of sleeping hours	1. From baseline visit to follow-up visit	No
Secondary	To determine the effect of the combination of the tDCS and PA on walking ability	Subjective walking ability with MSWS-12	1. Prior to treatment beginning 2. After treatment end 3. 4 weeks follow up	No
Secondary	To determine the effect of the combination of the tDCS and PA on fatigue	Perceived general fatigue with VAS- F ₀₋₁₀	1. Prior to treatment beginning	No

CONFIDENTIAL

This material is the property of the NYU School of Medicine and Langone Medical Center. Do not disclose or use except as authorized in writing by the study sponsor

Interventional Template Version: 28 APR 2017

			2. After treatment end 3. 4 weeks follow up	
Secondary	To evaluate the presence of adverse events and subjective pain during stimulation	Experience of AE and pain ratings with VAS-P ₀₋₁₀	1. After treatment end	Yes
Secondary	To determine the effect of the intervention tDCS+PA on processing speed	Change from baseline in processing speed (BICAMS, Cogstate Brief Battery)	4. Baseline 5. After treatment end 6. 4 weeks follow up	No

This section should contain all pertinent documents associated with the management of the study. The following lists a few examples of potential attachments:

- Investigator Agreement (for any investigator, other than sponsor-investigator, who participates in the study)
- Sample Consent Form
- Study Procedures Flowchart/Table
- Study Monitoring Plan

CONFIDENTIAL

This material is the property of the NYU School of Medicine and Langone Medical Center. Do not disclose or use except as authorized in writing by the study sponsor

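### The processing-speed endpoint is worded as an effect of aerobic exercise, which a trial where both arms exercise cannot estimate; it should be the active-versus-sham difference in change

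*Combined protocol and SAP*

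**What the plan says.** The endpoint in section 3.4.2 reads "Change in processing speed between baseline and immediately after the treatment end to assess improvement in cognitive function as indirect effect of aerobic PA". It names two time points and a cause, but no comparison of arms. The gait, questionnaire, fatigue-scale, EEG-session cognitive, ActiGraph and balance endpoints in the same list are all worded as active-versus-sham comparisons.

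Section 3.3 gives the design: "There will be a 1:1 random assignment of participants to receive either the active or the sham tDCS while performing the PA program". Section 4.9.1 confirms that physical training is part of both arms.

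The objectives table in section 15 (Attachments) describes the aim for the same measure differently: "To determine the effect of the intervention tDCS+PA on processing speed". The measure given there is "Change from baseline in processing speed (BICAMS, Cogstate Brief Battery").

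On testing, section 5.3.2 schedules "Cognitive assessment using BICAMS and CogState brief battery" at Baseline, and sections 5.3.4 and 5.3.5 repeat both batteries at Treatment End and at four weeks. BICAMS contains the SDMT (5.2.1). Participants chosen for the optional EEG take further tests; section 5.3.3 describes the recording as made "While performing cognitive tests (CogState and the SDMT) before and after the stimulation period".

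On analysis, section 7.1 states "There is a significant difference between active and sham groups by comparing primary and secondary outcomes at baseline and end treatment time". Section 7.2.1 sets an RM-ANOVA with tDCS (two levels) and Time (three levels) as the general approach. Section 7.2.3 lists specific analyses for TUG, sway and questionnaires. It does not list cognition.

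**The concern.** The endpoint asks whether exercise improved processing speed, and the trial has no comparator for exercise. Without one, the only evidence on that question is change over time. Such change can arise from exercise, from having taken the same test before, from expectation in people who know they are in a treatment study, or from regression to the mean. The design does not separate these.

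Practice deserves particular attention. The same tests are given before and after about two to three weeks of treatment, and the protocol describes no alternate forms or practice run for them. It does recognise familiarisation elsewhere: the first i-TUG trial is a warm-up and only the second is measured.

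At stake is a causal statement. A higher score at Treatment End could be reported as a cognitive benefit of exercise when test repetition alone might account for it.

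**Working it through.** **Step 1. What each term can estimate.** Let P be the mean effect of PA on the Baseline-to-Treatment-End change, D the added effect of active tDCS, and N the sum of practice, expectation and regression to the mean. With 1:1 allocation, and N the same in both arms on average:

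- Mean change, active arm: P + D + N
- Mean change, sham arm: P + N
- Difference (the group-by-time contrast between these visits): D
- Average over arms (the Time contrast): P + D/2 + N

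P never appears without N. The group-by-time contrast is free of N, but it is also free of P. No term of the planned model isolates an effect of PA. The joint effect of tDCS and PA named in section 15 is P + D, and it too appears only together with N.

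**Step 2. How often the tests are taken by Treatment End.** Without EEG, the SDMT is taken twice (BICAMS at Baseline and Treatment End), and so is Cogstate. With EEG the number is higher but cannot be fixed, because the documents place the EEG testing differently:

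- Section 5.2.1: "at the discretion of the study staff before and after the first and final tDCS session"
- Section 5.3.3: day 1 and day 11
- Section 4.4 visit table: Session 1, Session 9 and the Treatment-End Visit
- Section 15: Day 1 and Day 10
- Section 16: Baseline and the Treatment End Visit

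The section 5.2.1 reading, with every administration counted separately, gives 1 + 2 + 2 + 1 = 6 for the SDMT. That is an upper reading. When no ActiGraph is used, session 1 falls on the baseline day (4.4), and the documents do not say whether the BICAMS SDMT and the pre-session SDMT are then separate. Two administrations are enough for the argument.

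**Step 3. Illustration of size.** The plan gives no figure for processing speed to reproduce; its only sample-size calculation is for gait velocity.

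Inputs from the documents:

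- n = 72 evaluable participants (4.5: 80 × 0.9), or 36 per arm
- two-sided 5% test (7.2.1)

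Assumptions, because the documents give no figures:

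- P = 0 and D = 0
- practice gain g of 1, 2 or 3 points
- SD of change s of 5 to 7 points

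For a one-sample t-test on change, the noncentrality is λ = (g/s)·√n. The rejection probability is Pr(|T| > t₀.₉₇₅,ₙ₋₁), where T is noncentral t with n − 1 degrees of freedom. For example, with g = 1, s = 5 and n = 72, λ = 0.2 × 8.485 = 1.70, the critical value is 1.994 and the probability is 0.39. With s = 7, λ = 1.21 and the probability is 0.22.

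| Assumed gain | n = 72, s = 7 to 5 | n = 36, s = 7 to 5 |
|---|---|---|
| 1 point | 0.22–0.39 | 0.13–0.21 |
| 2 points | 0.67–0.92 | 0.39–0.65 |
| 3 points | 0.95–1.00 | 0.71–0.94 |

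**Step 4. The randomised contrast under the same conditions.** A simulation of 20,000 trials with 36 per arm, no PA or tDCS effect, and a practice gain of 0.2, 0.3 or 0.5 SD of change in both arms gave active-versus-sham rejection rates of 5.0% to 5.3%. The pooled before-after test rejected in 38%, 72% and 99% of the same trials.

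**The case against.** The strongest reply is that the protocol already has an active-versus-sham framework. Section 3 introduces all objectives as a comparison of active with sham stimulation, 7.1 states that hypothesis for secondary outcomes, and 7.2.1 applies a model with a tDCS factor. No section plans a pooled or within-arm before-after test. This stands, and it limits the consequence. A reader might infer that practice gain will be reported as an exercise benefit, or that the probabilities above are this protocol's error rates. The documents support neither reading. The misreading is something that could happen, and the probabilities describe a test that the plan does not explicitly include.

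The framework does not rescue the endpoint's stated purpose, though. The group-by-time term answers a question about tDCS. Anyone trying to answer the question actually written, about exercise, is left with the Time term. Because 7.2.3 omits cognition, nothing there settles which term is to be used.

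Two further points stand in part:

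- The section 15 row might be taken as independent evidence that a before-after analysis is intended. It is not: the gait, i-TUG and sway rows use the same stock wording, and their endpoints are explicitly active versus sham. The row does, however, attribute the effect to tDCS with PA, whereas 3.4.2 attributes it to PA.
- It is tempting to say that EEG participants take the SDMT six times, or that unequal exposure biases the arms. Six is only an upper reading. EEG is optional and chosen by staff who are meant to be blinded, so exposure need not differ by arm.

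**Conclusion.** The point holds in limited form. As worded in 3.4.2, the processing-speed endpoint asks for an effect of aerobic PA that this design cannot estimate, because both arms do the same PA. The trial can estimate the added effect of active tDCS over sham when both are given with PA. That conclusion follows from the design and needs no numerical assumption.

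The size of a possible false conclusion does rest on assumptions. If change over time were tested and credited to exercise, the probability of a spurious finding in 72 participants would run from about 0.22 to 1.00 over the assumed gains and SDs, against about 5% for the randomised comparison. That comparison stays near 5% provided practice is the same on average in both arms.

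This is one secondary endpoint in a pilot study. The primary endpoints, safety assessment and sample size are unaffected. The change should be made because it is nearly free and prevents an unsupported causal statement.

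**What to change.** 1. In 3.4.2, restate the endpoint as the active-versus-sham difference in change in processing speed from Baseline to Treatment End, in line with 7.1 and 7.2.1.
2. Base it on the BICAMS SDMT and Cogstate given at those two visits, and exclude the EEG-session repeats.
3. Delete the closing attribution to aerobic exercise. State that within-arm or pooled change is descriptive and uncontrolled.
4. Add cognition to the RM-ANOVA analyses listed in 7.2.3.
5. Reconcile the processing-speed row in section 15 with the new wording.

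No visit, test or participant is added. The downside is that the trial no longer claims an effect of PA on cognition, which its design cannot support.

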3.4.3 Exploratory Study Endpoint

As an optional measure, we will collect participants' electronic medical records, including MRI brain scans already collected during previous clinical visits, to evaluate whether there is a correlation between the degree of brain atrophy and the participants' clinical response to tDCS i.e., the level of improvement in gait, balance and cognitive measures after tDCS treatment. Previous studies showed inter-individual variability in response to tDCS treatment. One of the factors that affects biological response to electrical current was shown to be the degree of brain atrophy [Lucia et al., 2015; Mahdavi et al., 2018]. Recent studies based on human head model showed how brain characteristics such as total brain and grey matter volume can perturb the current distribution density throughout the brain [Mahdavi et al., 2018]. Specifically, reduced grey matter volume was associated with low magnitude of current density in the brain.

4 Study Enrollment and Withdrawal

4.1 Inclusion Criteria

In order to be eligible to participate in this study, an individual must meet all of the following criteria:

1. Age 18-70
2. Definite MS diagnosis, subtype relapsing-remitting (RR-MS) or secondary-progressive (SP-MS)
3. Expanded Disability Status Scale (EDSS) from 1 to 6.5 with clinically significant gait deviations
4. Clinically stable

CONFIDENTIAL

This material is the property of the NYU School of Medicine and Langone Medical Center. Do not disclose or use except as authorized in writing by the study sponsor

Interventional Template Version: 28 APR 2017

5. Able to independently walk with or without an assisting device (i.e. cane, crutches or walking frames) for medium-long distance
6. Absence of other associated medical conditions that would prevent participants from performing physical activity, such as cardiorespiratory and severe osteoarticular disorders
7. Able to use study equipment
8. Able to commit to 10 sessions of tDCS while performing physical program with baseline and follow-up visits
9. Able to understand the informed consent process and provide consent to participate in the study
10. Stable and continuous access to internet service at home
11. Adequate home facilities (enough space, access to quiet and distraction free area)

4.2 Exclusion Criteria

An individual who meets any of the following criteria will be excluded from participation in this study:

1. Visual, auditory and motor deficits that would prevent full ability to understand study, as judged by treating neurologist or study staff
2. Primary psychiatric disorder that would influence ability to participate
3. Receiving current treatment for epilepsy
4. Uncontrolled headaches and migraines. In addition, if a subject has had a change in the rate or severity of head pressure, headache, or migraine in the past two weeks, they are excluded
5. History of head trauma (e.g., head injury, brain surgery) or medical device implanted in the head (such as Deep Brain Stimulator) or in the neck (such as a Vagus Nerve Stimulator)
6. Any skin disorder/sensitive skin (e.g., eczema, severe rashes), blisters, open wounds, burn including sunburns, cuts or irritation, or other skin defects which compromise the integrity of the skin at or near stimulation locations (where electrodes are placed)
7. Treatment for a communicable skin disorder currently or over the past 12 months
8. History of uncontrolled or labile hypertension
9. Other serious uncontrolled medical condition (e.g. cancer or acute myocardial infarction)
10. Wide Range Achievement Test-4th Edition (WRAT-4) Reading Recognition scaled score < 85
11. History of clinically significant abnormalities on electrocardiogram (EKG)
12. Presence of chronic medical illness and/or severe ataxia
13. Botulinum toxin injection within the past 4 months
14. Functional surgery for lower limb in the past 6 months (e.g. hip or knee replacement)
15. Alcohol or other substance use disorder
16. Pregnant or breastfeeding

